3.6 Informed Consent

Consent forms describing in detail the study intervention, study procedures, and risks are given to the participant and written documentation of informed consent is required prior to starting intervention/administering study intervention. Potential participants will be offered the following consent materials are submitted with this protocol: consent form.

3.6.1 Screening (if applicable)

The PI and RA will be responsible for performing all screening activities. After receiving training from the investigative team faculty, the RA will screen each weekday a dedicated Epic report that identifies adult inpatients hospitalized on medicine units at Yale-New Haven Hospital YSC and SRC who are on the YNHH Opioid Registry and have not opted out of research in the YNHHS. Charts of each patient on the Epic report will be reviewed to confirm absence of exclusion criteria. The RA will consult the PI with any questions regarding eligibility. Data on the number of patients screened and number of eligible patients will be recorded in daily screening logs in REDCap for recruitment tracking purposes.

3.6.2 Recruitment, Enrollment and Retention (if applicable)

Eligible patients will be approached by the RA during hospitalization. The RA will first check in with the clinical team (e.g., charge nurse) to confirm appropriateness and timing of approach.

The RA will provide an overall description of the study and gauge the patient's interest. If the patient is potentially interested in participating, the RA will begin the informed consent process- this will include providing details about the structure and format of study participation, the disclosure of potential benefits and risks, and confirmation that study participation is completely voluntary and will not in any way affect the care the patient receives at YNHSS or elsewhere. The patient will be provided with a paper consent form to review with the RA and will be given ample time to review independently or with family members. The patient will then be provided an opportunity to ask questions about the study. Once the RA has answered all questions, the participant will be asked to sign the informed consent form, indicating their understanding and willingness to participate in the study. The consent form will be scanned into REDCap for record keeping. A copy of the form will be given to the participant to keep. Study participation will commence after the signing of the informed consent form and will last until 30 days after discharge from the hospitalization during which the participant was enrolled in the study.

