1.5 Potential Risks and Benefits

1.5.1 Potential Risks

Opioid Stewardship Intervention: The goal of the enhanced opioid stewardship intervention is to manage chronic pain while reducing risk of inappropriate/risky opioid use and preventing harms of opioid use. We anticipate no significant adverse effects from participating in the opioid stewardship intervention. It is important to note that the intervention team will not have a direct impact on patient care; all guidance related to appropriate pain management and adjuvant therapies will be provided to a participant’s clinical team, who will be ultimately responsible to decide whether to apply such guidance to their patient’s care. Nonetheless, there is a small chance that efforts to manage pain in the context of best practices for opioid use may inadvertently and temporarily result in distress in

participants. Distress may include temporary increases in pain or physical or mental discomfort from opioid withdrawal symptoms. All patients will receive best practice treatment for their withdrawal symptoms and treatment of OUD, if present, as part of usual clinical care.

Rating scales and questionnaires: Rating scales and questionnaires are all non-invasive, however, some questions may be distressing to participants.

Confidentiality: There is a small risk of a breach of data or private information associated with participation in this study.

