2.1 Hypothesis

Participants randomized to the intervention will have less pain, fewer opioid-related adverse events, and greater improvement in quality of life compared with control participants, as measured at hospital discharge.

The care of intervention participants will also include a greater number of guideline-based care elements for opioid stewardship compared with the care of control participants, as measured at hospital discharge.

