2.3 Secondary Objective (if applicable)

There are two secondary objectives to this pilot RCT, both related to efficacy.

One secondary objective is to determine whether an enhanced opioid stewardship program increases use of guideline-based opioid care. The other secondary objective of this study is to determine whether an enhanced opioid stewardship program reduces pain frequency, intensity, and interference and decreases the risk for opioid-related adverse events among

adult patients with chronic pain hospitalized on medical units at Yale-New Haven Hospital, York Street and Saint Raphael campuses. Outcomes for the secondary objectives are described in section 3.2.2.

3 Study Design

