3.4 Study Procedures

All patients will receive standard hospital care. Patients who are identified as eligible for the study via screening in Epic will be approached during hospitalization, undergo informed consent, and be enrolled in the study. Those who consent will be asked questionnaires

related to patient reported outcomes of pain, anxiety, depression and quality of life at baseline. Patients will then be randomized on a 1:1 ratio to either the enhanced opioid stewardship program arm or a control (i.e., usual care) arm. Patients who are randomized to the intervention arm will have their medical record reviewed by both a pharmacist and a physician trained in pain and addiction medicine. The pharmacist and physician will provide best practice guidance via an Epic note to the primary care teams to consider, versus continuation with their usual care plan. All guidance will be voluntary for clinical teams to follow. All participants will be tracked daily in Epic for discharge status, and when discharge within 48 hours is anticipated, the study team will perform the final patient interview, which will be very similar to the baseline interview and composed of questionnaires related to pain, anxiety, depression, and quality of life. Medical record abstraction will be performed to abstract relevant characteristics of each participant's hospitalization, use of guideline-based best practices for pain management and opioid stewardship at discharge, and incidence of readmissions and ED visits within 30 days after discharge for the hospitalization during which the participant was recruited.

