3.5 Study Schedule

The total number of visits as part of this intervention will include (1) screening and consent, (2) baseline interview (may be combined with consent visit, per participant's preference), and (3) a peri-discharge interview (within 48 hours of anticipated discharge). The total number of study visits is expected to be three per participant, with the potential for greater frequency of interaction via phone. Each visit will last approximately 30 minutes or less.

Study Schedule:

Study Activity	Time frame/duration
1. Currently hospitalized patients screened in Epic	Every weekday
2. Eligible participants approached by study team	Every weekday
3. Study described, questions answered, written informed consent obtained	30 minutes
4. Participant completes baseline interview; \$25 gift card provided	15 minutes
5. Participant randomized to intervention or usual care arm	1 minute
6. Participant's hospitalization tracked for anticipated discharge status	Daily
7. Intervention participants' charts reviewed by study team's addiction medicine physician/pharmacist for adherence to best practice guidelines for pain management/opioid stewardship.	Once, within 24 hours of randomization
8. Study addiction medicine physician composes note in intervention participant's medical record with recommendations to optimize guideline-based pain management/opioid stewardship	Once
9. Study addiction medicine physician alerts primary clinical care team via Mobile Heart Beat of Epic note regarding guideline-based care recommendations	Once
10. Final participant interview performed within 48 hours of anticipated discharge; \$25 gift card provided	15 minutes
11. Medical record abstraction performed for hospitalization characteristics, use of guideline-based best practices for pain management/opioid stewardship, and readmissions/ED visits within 30 days	1-30 days post-discharge

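### The consent assurance in section 3.6.2, read literally, says participation cannot affect care, whereas the protocol expects care in the intervention arm may change; limit the assurance to the patient's decision

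*Combined protocol and SAP*

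**What the plan says.** Section 3.6.2 sets out the consent conversation. The research assistant explains how participation works, discloses benefits and risks, and gives "confirmation that study participation is completely voluntary and will not in any way affect the care the patient receives at YNHSS or elsewhere".

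Elsewhere the protocol describes an intervention meant to act on care:

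- Section 2.1 (Hypothesis): "The care of intervention participants will also include a greater number of guideline-based care elements for opioid stewardship", compared with control participants.
- Section 2.3 (Secondary Objective): one aim is "to determine whether an enhanced opioid stewardship program increases use of guideline-based opioid care".
- Section 3.5 (Study Schedule): after a chart review and a note in the record, "Study addiction medicine physician alerts primary clinical care team via Mobile Heart Beat of Epic note regarding guideline-based care recommendations".
- Section 1.5.1 (Potential Risks): with a probability described as small, "efforts to manage pain in the context of best practices for opioid use may inadvertently and temporarily result in distress". The section then says what this could involve: "Distress may include temporary increases in pain or physical or mental discomfort from opioid withdrawal symptoms".
- Section 3.4.2 (Adverse Events): participants are monitored for reactions to something the study team recommended, with a new medication as the example.

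Two statements limit this. Section 1.5.1 says that "the intervention team will not have a direct impact on patient care", and section 3.4 says: "All guidance will be voluntary for clinical teams to follow".

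**The concern.** The familiar assurance at consent is that a patient's choice to join, decline or leave a study carries no penalty in their care. The clause in 3.6.2 says something different: that being in the study has no effect on care of any kind. The trial exists to see whether an enhanced program can alter the care of individual patients, so a research assistant who followed the clause literally would be giving an absolute reassurance that the design does not support.

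The stake is participant protection. Whether pain and opioid treatment may change because of the study is material to a hospitalized patient with chronic pain and opioid dependence who is deciding whether to enrol.

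**Working it through.** No power, error rate or effect size bears on this point, so the check is a comparison of texts plus one count.

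**1. What the clause asserts.** Its grammatical subject is study participation. Its scope is absolute: it excludes any effect on care, direct or indirect.

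**2. What the rest of the protocol expects.**

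| Section | Content | Compatible with no effect of any kind? |
|---|---|---|
| 2.1 | More guideline-based elements in intervention care | No |
| 2.3 | Increased guideline-based care is a secondary objective | No |
| 3.4, 3.5 | Chart review, note in the record, alert to the treating team | No, where the advice is followed |
| 1.5.1 | Small chance of temporary pain or withdrawal discomfort | No |
| 1.5.2 | Benefits expected mainly in the intervention group | No |
| 3.4.2 | Monitoring for reactions to a recommended treatment | No |
| 1.5.2, 3.4 | Control group receives usual care | Yes |

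**3. Whether the limiting statements remove the conflict.** Section 1.5.1 denies only a direct impact, because the clinical team decides. Section 3.4 makes the guidance optional for clinicians. Together they make the effect on care indirect and conditional on uptake. Neither makes it nil, and only a nil effect would fit the clause.

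**4. When the statement is made.** Under sections 3.4 and 3.5, consent and the baseline interview come before randomization. The arm is therefore unknown when the assurance is given. With 1:1 allocation, each consenting patient has a one-in-two chance of the arm in which care may change.

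**5. Count.** Section 3.3.1 plans 100 participants, and 100 × 1/2 = 50, matching the approximately 50 per arm stated there. The instruction applies to all 100 enrolled, and also to anyone who hears it and then declines, a number the documents do not give. About 50 is the number assigned to the intervention. It does not count patients whose care will actually change, since that depends on uptake.

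**6. What else the patient is told.** Section 3.6.2 requires disclosure of benefits and risks in the same conversation. Section 3.6 says the consent form covers the intervention, the procedures and the risks in detail. A patient would therefore receive both an accurate account of the intervention and an absolute statement inconsistent with it.

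**The case against.** The strongest reply is that nobody would read the clause literally. It is attached to the statement that participation is voluntary, and it extends to care outside the hospital system. That extension suits a no-penalty promise better than a claim about a note in one admission's chart. Section 4.1 states the same principle for withdrawal, which is to be without prejudice. Section 3.6.2 also summarizes topics rather than giving a verbatim script, and the consent form is not in the documents.

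Most of this stands. The intent was very probably the ordinary assurance, and what patients read cannot be judged from here. But 3.6.2 is the protocol's instruction for the conversation, and it does not say what was probably meant. Likely intent makes the correction easy without making it unnecessary.

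It can also be said that the effect on care is indirect, that section 1.5.1 anticipates no significant adverse effects, and that the hypothesis concerns an average difference rather than every patient. These points stand too and limit the seriousness. They do not make the absolute wording accurate.

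A reader might go further and infer that participants would under-report new pain or withdrawal symptoms. The documents do not support that. Section 3.4.2 has the study team monitor for reactions to recommended treatments and for pain increases on routine hospital ratings, and section 3.6.3 repeats the pain questions near discharge. None of this is described as depending on the patient linking a symptom to the study.

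**Conclusion.** The inconsistency is real but narrow. One clause in section 3.6.2, followed as written, gives an inaccurate absolute reassurance on a point material to consent. It applies to all 100 planned participants, and it conflicts with the design through the intervention arm of about 50. For the control arm, which receives usual care, it is consistent.

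Two stronger conclusions might be drawn, and neither is supported. The first is that patients are misled or uninformed: sections 3.6 and 3.6.2 require the intervention and its risks to be disclosed, so the result is a mixed message. The second is that use of the trial data is in jeopardy: nothing in the documents points that way.

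The conclusion assumes that the research assistant follows 3.6.2 as worded. It concerns the protocol's instruction only and says nothing about the wording of the consent form. The estimates, the analyses and the sample size are untouched.

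**What to change.** Replace the clause in 3.6.2 with two statements:

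1. Taking part is voluntary, and the patient's decision to take part, decline or withdraw will not affect the care they receive.
2. If the patient is assigned to the intervention, their clinical team will receive advice that may change pain and opioid care, with the risks already listed in section 1.5.1.

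Then check that the consent form, and any script or training material the research assistant uses, says the same.

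The cost is one amendment to the Yale HIC and two sentences of text. A few more patients may decline once the statement is accurate; the documents give no basis for estimating how many.

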3.6.3 Study Visits (if applicable)

There will be up to 3 study visits with each participant, which will take place during hospitalization or in the first week after hospital discharge.

The first study visit will be for recruitment and enrollment. This visit will follow the format described in Section 3.6.2. This visit will last approximately 30 minutes.

The second study visit will be for completion of the baseline interview. This study visit may occur directly after enrollment. During this interview, participants will be asked questions related to pain, depression, and anxiety. Pain will be assessed using an abridged version of the Brief Pain Inventory,¹ which will take 5 minutes to complete. Depression and anxiety will be assessed with the Patient Health Questionnaire-4,² which will take 2 minutes to complete. They will also be asked demographic questions, for descriptive purposes. The baseline interview visit will last approximately 15 minutes.

The third study visit will be for completion of the final interview, which will take place within 48 hours of anticipated discharge. Participants will answer questions identical to those asked in the baseline interview on pain, depression, and anxiety. They will also be asked one question regarding their satisfaction with pain: "How pleased are you with your pain outcome during this hospital visit?", which will be answered on a Likert-type scale. The final interview will last approximately 15 minutes.

3.7 Statistical Method

3.7.1 Statistical Design

The design of this study is a randomized controlled trial. Due to the pilot nature of this trial, statistical considerations will consist primarily of bivariate analyses (i.e., t-tests, rank sum, and chi-square tests, as appropriate to variable type) to ensure balance of covariates

between randomization groups and also to explore unadjusted associations between randomization groups and our outcomes. Exploratory regression analyses may be utilized to evaluate multivariable-adjusted associations between randomization groups and our outcomes, particularly if an imbalance between covariates among randomization groups is discovered.

3.7.2 Sample Size Considerations

This pilot trial was not developed with power in mind to find a particular effect size in outcomes between study arms; hence we do not include power calculations.

3.7.3 Planned Analyses

Due to the pilot nature of this trial, statistical considerations will consist primarily of bivariate analyses (i.e., t-tests, rank sum, and chi-square tests, as appropriate to variable type) to ensure balance of covariates between randomization groups and also to explore unadjusted associations between randomization groups and our outcomes. Exploratory regression analyses may be utilized to evaluate multivariable-adjusted associations between randomization groups and our outcomes, particularly if an imbalance between covariates among randomization groups is discovered.

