3.2.2 Secondary and Exploratory Outcome Variables (if applicable)

A secondary outcome for this pilot RCT will include a count of guideline-based care elements considered to be “best practices” for opioid stewardship in the setting of chronic pain. These include ordering of alternative pain relief medications (e.g., acetaminophen), ordering of a bowel regimen, ordering of medication to treat opioid use disorder, order of urine toxicology screen, ordering of ECG for patients prescribed methadone, avoidance of co-prescriptions of benzodiazepines, and other associate “best care” practices. These metrics will be abstracted from the medical record.

Other secondary outcomes will include pain frequency, intensity, and interference, assessed using a modified Brief Pain Inventory.¹ Depression and anxiety will be measured using the Patient Health Questionnaire-4.² Participant satisfaction with pain care will also be assessed

at discharge. ED visits and readmissions at the 30 days post-discharge from the hospitalization in which the participant is recruited will also be abstracted from the medical record.

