3.3.1 Number of Participants

We anticipate 10-50 records will be returned in the Epic report each day that will be screened for eligibility. We aim to recruit 100 participants who meet all inclusion and exclusion criteria for the trial, for a total of approximately 50 each in the intervention and control arms. Screening and enrollment will continue until the target sample size has been reached, with a goal of recruiting 5-10 patients per week.

Eligibility Criteria/Vulnerable Populations

In order to be eligible for inclusion in the study, an individual must meet all of the following criteria:

- adults (age ≥ 18 years);
- admitted at YNHH (YS and SRC) on medical units;
- identified as having chronic pain and prescribed opioids.
- Have opioid dependence (evidenced by ongoing opioid prescription, meeting DSM-5 criteria for OUD, or clinical history)

Any individual who meets any of the following criteria will be excluded from participation in this study:

- active cancer
- current pregnancy
- hospice care/comfort measures only
- admission to inpatient psychiatry
- completed or planned Addiction Medicine consult during hospitalization

4. Study Methods/Procedures

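### Pain and PHQ-4 are compared mainly by unadjusted tests although the same scores are taken before randomization; prespecified baseline adjustment would give tighter estimates, at moderate correlation, from data already planned.

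*Combined protocol and SAP*

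**What the plan says.** Sections 3.7.1 and 3.7.3 of the combined protocol and SAP carry the same text. The lead analyses are t, rank-sum and chi-square tests, used "to ensure balance of covariates between randomization groups and also to explore unadjusted associations between randomization groups and our outcomes". Adjustment is discretionary: "Exploratory regression analyses may be utilized to evaluate multivariable-adjusted associations between randomization groups and our outcomes", and this "particularly if an imbalance between covariates among randomization groups is discovered". No covariate is named. Section 3.7.4 applies the same family of tests to baseline characteristics.

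The baseline scores exist before allocation. Section 3.4 has consenting patients answer questionnaires "related to patient reported outcomes of pain, anxiety, depression and quality of life at baseline. Patients will then be randomized on a 1:1 ratio". The schedule in 3.5 lists the baseline interview as item 4 and "Participant randomized to intervention or usual care arm" as item 5. Section 3.6.3 says the pain, depression and anxiety questions at the final interview are identical to those at baseline.

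On which score is analysed, section 2.1 expects that intervention participants "will have less pain, fewer opioid-related adverse events, and greater improvement in quality of life compared with control participants, as measured at hospital discharge". For pain, this points to the discharge score. Section 3.2.2 says only "Depression and anxiety will be measured using the Patient Health Questionnaire-4". The statistical section does not say, for either outcome, whether the discharge score or the change from baseline is compared.

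**The concern.** When an outcome is measured on the same scale before randomization and at follow-up, the baseline value is usually the best available predictor of the follow-up value. Conditioning on it removes outcome variance unrelated to treatment. That gain comes from the correlation and does not depend on whether the arms happen to differ at baseline. A plan that adjusts mainly when imbalance turns up ties the adjustment to the wrong feature of the data. It also leaves the choice of model and covariates until after the data have been seen.

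The stated purpose of the baseline tests is a separate difficulty. Under randomization any baseline difference is due to chance, so a significance test of it answers no open question, and a non-significant result does not show that the difference is negligible. Such tests cannot secure balance.

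At stake is the usefulness of the preliminary-efficacy estimates, which section 4.15 sends to a manuscript and to later grant applications. Section 3.7.2 disclaims any power target, so interval width is the appropriate yardstick.

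**Working it through.** The plan states no SD, effect size, significance level or precision target for pain or PHQ-4, so there is no figure of its own to reproduce.

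**Inputs**
- From section 3.3.1: sample size "for a total of approximately 50 each in the intervention and control arms", so n = 50 per arm.
- Assumed: a two-sided 95% interval; SD = 1 at both times, so results are in SD units.
- Assumed: baseline-to-discharge correlation r, varied from 0 to 0.7.
- Assumed, as a sensitivity check only: 40 completers per arm. The documents give no dropout rate.

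**Formulas for the half-width**
- Unadjusted discharge score: t(0.975; 2n−2) × √(2/n). With n = 50 this is 1.984 × 0.2 = 0.397.
- ANCOVA: t(0.975; 2n−3) × √[(2/n)(1−r²)(1 + 1/(2n−4))]. The last factor, 1 + 1/96 here, is the cost of estimating the slope.
- Unadjusted change score: t(0.975; 2n−2) × √[(2/n) × 2(1−r)].

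**Results, n = 50 per arm**

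| r | Unadjusted discharge score | ANCOVA | ANCOVA against unadjusted discharge score | Unadjusted change score |
|---|---|---|---|---|
| 0 | 0.397 | 0.399 | 0.5% wider | 0.561 |
| 0.1 | 0.397 | 0.397 | no difference | 0.532 |
| 0.2 | 0.397 | 0.391 | 1.5% narrower | 0.502 |
| 0.3 | 0.397 | 0.381 | 4.1% narrower | 0.470 |
| 0.5 | 0.397 | 0.346 | 12.9% narrower | 0.397 |
| 0.7 | 0.397 | 0.285 | 28.2% narrower | 0.307 |

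The normal approximation, 1.96 × √(1−r²) × √(2/50), gives 0.392 unadjusted and 0.384, 0.374, 0.339 and 0.280 at r = 0.2, 0.3, 0.5 and 0.7. These are 2.0%, 4.6%, 13.4% and 28.6% narrower.

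A simulation of 4,000 trials at each r gave ratios of adjusted to unadjusted width of 1.005, 1.000, 0.959, 0.871 and 0.717 at r = 0, 0.1, 0.3, 0.5 and 0.7, in agreement with the table.

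**Equivalent sample size.** In large-sample terms, ANCOVA on 100 participants matches an unadjusted comparison on 100/(1−r²): 110 at r = 0.3, 133 at r = 0.5 and 196 at r = 0.7.

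**Fewer completers.** With 40 per arm the unadjusted half-width is 0.445, and ANCOVA gives 0.428, 0.388 and 0.320 at r = 0.3, 0.5 and 0.7. At r = 0.5 this is 12.8% narrower, against 12.9% with 50 per arm, so the proportional gain hardly depends on retention.

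**Balance tests.** With 50 per arm and an assumed 5% level, the largest non-significant baseline difference is 1.984 × 0.2 = 0.397 SD. A difference of about 0.40 SD can therefore pass the check. This shows what the test cannot do. It is not an extra error, because chance imbalance is already reflected in the unadjusted interval.

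**The case against.** The strongest reply is that this is a feasibility pilot. Its primary outcomes are descriptive, it disclaims any target effect size, and it ties the simple analysis to its pilot nature. The unadjusted test is valid, and no go/no-go rule or sample size depends on the interval for pain or PHQ-4. That stands as a limit on importance, but preliminary efficacy is in the title, reducing pain is a secondary objective, and the results are meant for onward use.

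The size of the gain rests on a correlation the documents do not supply, and there are reasons it might be low. Patients are admitted for any medical condition, they enroll on varying hospital days, and the interval to the final interview is not fixed. This also stands: a material gain is not assured. But the trade is lopsided, with about 0.5% in width lost at zero correlation against 13% gained at 0.5.

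The comparator could be a change score, since the statistical section does not exclude one. The gain at r = 0.7 would then be smaller, about 8% by the normal approximation (0.304 to 0.280 SD). At r = 0.5 it would be the same 13%, and at r = 0.3 larger, about 19%. ANCOVA was the more precise at every correlation examined, so the direction holds.

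Regression is already permitted, and its use is not strictly confined to imbalance. True, but an optional model without named covariates secures neither the precision nor protection against a choice made after seeing the data.

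Two further points stand. The plan names tests and no confidence intervals, so reporting an interval is part of the proposal. The items and scoring of the abridged pain inventory are not in the document, so whether ANCOVA suits each item cannot be checked, and no gain was computed for ordinal models or against the rank-sum test.

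**Conclusion.** The concern holds as an efficiency point. Nothing in the planned comparison is biased or invalid; what is lost is precision. The loss is negligible if the correlation is about 0.2 or below, small at 0.3 and material from about 0.5. These figures rest on the assumed correlation, equal SDs at both times, close-to-continuous scores and a discharge-score comparator.

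It applies to pain and PHQ-4 only. Satisfaction, the count of guideline-based care elements, and 30-day ED visits and readmissions have no baseline value of the same measure. Using imbalance as the prompt for adjustment, and leaving the analysed score unstated, are gaps in prespecification whatever the correlation proves to be. The change is recommended; it is not a condition for the trial's primary purpose.

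**What to change.** In sections 3.7.1 and 3.7.3, replace the optional, imbalance-prompted regression with a statement such as:

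*Whatever the observed balance, peri-discharge pain intensity, pain interference and PHQ-4 scores will be compared between arms by ANCOVA with the baseline value of the same scale as covariate, and reported as an adjusted difference with 95% CI and the number analysed per arm.*

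This also settles that the discharge score is the one analysed. For pain frequency, and for any item of the abridged inventory that is not close to continuous, name a baseline-adjusted model suited to the scale, such as ordinal regression. Keep the unadjusted comparison as supportive. In section 3.7.4, present baseline characteristics descriptively by arm and drop significance tests as a trigger for adjustment.

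The cost is SAP wording only: no new data, visits or participants, since both scores are already collected. ANCOVA on completers is still a complete-case analysis, so this change does not address the absence of missing-data handling in section 3.7.6.
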